***Design***

Patients who voluntarily agreed to participate in the study were randomly assigned into two groups. Patients enrolled in the study were referred for an initial consultation with a dietitian following their diagnosis by a gastroenterologist. The energy-restricted diet group followed an energy-restricted diet for 8 weeks, while the energy + time-restricted diet group followed the same diet and a 16:8 eating pattern and restricted food intake to an 8 h window each day. The effectiveness of the intervention was assessed using anthropometric and biochemical measurements, and Fibroscan investigations were performed before the intervention (T0) and after the intervention (T8).

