Official Title of the study: Effects of Intermittent Fasting in Metabolic Dysfunction Associated Fatty Liver Disease

NCT number: NCT06664684

Date of the document: 06.05.2022

Statistical Analysis Plan

Study data were analyzed using SPSS 28.0 software suit. Statistical significance was set at $p < 0.05$ for all analyses. Data were checked for normality of distribution using the Kolmogorov–Smirnov test. Categorical variables were analyzed using the chi-square test. Median (Quartile 1–Quartile 3) values were used in descriptive statistics. The Mann–Whitney U test was used to determine whether the baseline values were similar between the two groups before the intervention. The before/after comparison of the quantitative data was performed using the Wilcoxon test.

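### The SAP tests for baseline similarity with a Mann–Whitney test, which cannot establish it, so a chance imbalance may go unaddressed when the two arms are contrasted

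*SAP*

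**What the plan says.** The Protocol (Design) says patients were "randomly assigned into two groups". Both arms received the same energy-restricted diet for 8 weeks, and "the energy + time-restricted diet group followed the same diet and a 16:8 eating pattern". Measurements were taken at T0 and T8.

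The SAP is a single paragraph. On baseline it says: "The Mann–Whitney U test was used to determine whether the baseline values were similar between the two groups before the intervention". On the threshold it says: "Statistical significance was set at $p < 0.05$ for all analyses". For quantitative outcomes it names one analysis: "The before/after comparison of the quantitative data was performed using the Wilcoxon test". It does not say whether that is done separately by arm; I take it to be so. Descriptive statistics are medians with quartiles, and categorical variables are analysed with a chi-square test whose purpose is not specified.

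The documents give no sample size, no margin defining similarity, no standardised difference, no baseline adjustment and no between-arm comparison of T8 values or of change.

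**The concern.** The stated purpose of the baseline test is to establish similarity. The only criterion available is p < 0.05, so p ≥ 0.05 is the only result that could be read as similar. The SAP does not write that rule out; it is an inference from the purpose and the threshold together.

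Read that way, the test fails in both directions. A non-significant result depends heavily on group size and says little about whether the observed difference matters for the outcome. A significant result, if randomisation was sound, is a false alarm about the allocation, and it may cast doubt on a sound trial or invite adjustment for whichever variable happened to be flagged.

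What is at stake is the comparison of 16:8 eating with the same diet alone. Body weight, steatosis and serum markers at T8 can be expected to depend on their T0 values. The baseline test is the only between-arm test that the SAP names for quantitative data, and nothing else in it deals with imbalance. A reader who contrasts the two arms' before/after results would lean on a finding of similarity that the test cannot supply.

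**Working it through.** The plan has no figure of its own to reproduce.

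**Inputs.** From the documents: random allocation to two groups, measurements at T0 and T8 (Protocol, Design), and a 0.05 threshold for all analyses (SAP). Assumed, because not stated: equal arms of n = 15 to 100, a two-sided test, roughly normal data with equal SD at T0 and T8, and a T0–T8 correlation ρ of 0.5 to 0.8.

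**Step 1: largest observed imbalance that stays non-significant.** By the t approximation, d = t(0.975, 2n − 2) × √(2/n), in SD units. Using instead the normal quantile and the large-sample efficiency of the Mann–Whitney test (3/π) gives 0.73, 0.63, 0.52, 0.40 and 0.28, so the approximation is adequate.

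**Step 2: how often chance produces a given imbalance under sound randomisation.** For one variable, P(|d| > c) = 2 × [1 − Φ(c / √(2/n))].

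| n per arm | Step 1: limit (SD) | Step 2: above 0.3 SD | Step 2: above 0.5 SD |
|---|---|---|---|
| 15 | 2.048 × 0.365 = 0.75 | 41% | 17% |
| 20 | 2.024 × 0.316 = 0.64 | 34% | 11% |
| 30 | 2.002 × 0.258 = 0.52 | 25% | 5% |
| 50 | 1.984 × 0.200 = 0.40 | 13% | 1% |
| 100 | 1.972 × 0.141 = 0.28 | 3% | under 0.1% |

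The columns must be read together. A 0.5 SD imbalance stays non-significant at 15, 20 and (just) 30 per arm, but would be flagged at 50 or 100.

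**Step 3: what an imbalance does to a between-arm contrast.** Let Δ be the observed T0 difference between arms.
- Unadjusted T8 difference: expected shift ρ × Δ. For Δ = 0.5 SD: 0.5 × 0.5 = 0.25 to 0.8 × 0.5 = 0.40 SD.
- Difference in change: expected shift (ρ − 1) × Δ. For Δ = 0.5 SD: −0.5 × 0.5 = −0.25 to −0.2 × 0.5 = −0.10 SD, the opposite direction.
- T8 adjusted for T0 in a linear model: 0, whatever the baseline p-value.

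At 100 per arm, the largest imbalance that passes (0.28 SD) gives 0.14 to 0.22 SD for T8 and 0.06 to 0.14 SD the other way for change.

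**Step 4: false alarms.** With k independent baseline variables, P(at least one p < 0.05) = 1 − 0.95^k, which is 40% for k = 10 and 64% for k = 20. The number of variables is assumed. Anthropometric and liver measures are probably correlated, so the independence figures are likely to be too high.

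**Step 5: could similarity be tested properly?** Two one-sided tests at 5% each, with 80% power and a true difference of 0, need n = 2 × [(1.645 + 1.282)/margin]² per arm: 69 for ±0.5 SD, 191 for ±0.3 SD and 429 for ±0.2 SD. The margins are assumed. In a randomised trial this would cost a great deal and answer a question that adjustment makes unnecessary.

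**The case against.** The strongest reply is that the test does nothing in the plan as written. The SAP attaches no adjustment, exclusion or choice of analysis to its result. The Wilcoxon test compares each patient with his or her own T0 value, so a difference between arms at baseline does not enter it. Deleting the Mann–Whitney sentence would change no outcome result. The medians and quartiles already let a reader see an imbalance. The larger gap is the missing between-arm analysis.

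Most of this stands, and it limits the point. A reader might infer that the baseline test acts as a gate deciding whether T0 is adjusted for; the SAP does not say so. A reader might also infer that the 16:8 comparison has been distorted. The documents contain no baseline data and no sample size, and imbalance could act only through an informal contrast of the two arms' before/after results or through an analysis added later. It would also be wrong to argue from the test's power to detect a true baseline shift: with sound random allocation no such shift exists, and the relevant quantity is the chance imbalance in Step 2. Nor does chance imbalance inflate the overall type I error of a valid between-arm test; the harm is bias conditional on the imbalance that occurred, and lost precision.

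What the reply does not remove is that the SAP assigns the test a purpose it cannot serve. That would remain so if a between-arm analysis were added.

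**Conclusion.** The point holds as a moderate one that should be corrected. A Mann–Whitney test at p < 0.05 cannot determine that randomised arms were similar at baseline, and this is true at any sample size.

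The practical size depends on a group size the documents do not give. At 15 to 30 per arm, imbalances of about half to three quarters of an SD would pass, and imbalances above 0.3 SD would be common (25% to 41% of trials for any one variable). At 100 per arm the exposure is small. The resulting shift depends on which contrast is made and reverses direction between T8 values and change. These sizes rest on equal arms, roughly normal data, equal SDs at both times and the assumed correlation range.

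The supportable conclusion is that a relevant imbalance may go unaddressed. That one occurred, or that it altered a result, cannot be read from these documents.

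**What to change.** In the SAP:

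1. Delete the baseline Mann–Whitney test, together with any chi-square test applied to baseline characteristics (the SAP does not say whether chi-square is used for that).
2. Present baseline by arm as median and quartiles, add standardised differences, and give no p-values.
3. Specify a between-arm comparison of each outcome at T8 that adjusts for its T0 value, for example ANCOVA or a rank-based version, whatever imbalance is observed.
4. State that no adjustment decision depends on a baseline p-value.

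The cost is a few sentences in the SAP and one column in the baseline table. T0 and T8 values are already collected, so no new data are needed. The SAP is written in the past tense; if the analysis has already been run, the adjusted comparison can still be done but should be dated and labelled as added afterwards.

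### The SAP states no between-arm comparison of any quantitative outcome after treatment, so the effect of adding 16:8 eating is never tested or estimated

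*SAP*

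**What the plan says.** The Protocol (Design) sets up a randomised parallel comparison: "Patients who voluntarily agreed to participate in the study were randomly assigned into two groups". Both arms receive the energy-restricted diet for 8 weeks, and "the energy + time-restricted diet group followed the same diet and a 16:8 eating pattern". It then says how benefit is judged: "The effectiveness of the intervention was assessed using anthropometric and biochemical measurements", with Fibroscan, at T0 and T8.

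The SAP is a single paragraph. Its two-group test for quantitative data is tied to baseline: "The Mann–Whitney U test was used to determine whether the baseline values were similar between the two groups before the intervention". Its test of change is "The before/after comparison of the quantitative data was performed using the Wilcoxon test", and it does not say whether this is run in each arm or in all patients together. For other data it says "Categorical variables were analyzed using the chi-square test", without naming variables, groups or a time point. The threshold is common to everything: "Statistical significance was set at $p < 0.05$ for all analyses".

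**The concern.** The arms differ by design only in the 16:8 window. The effect of 16:8 can therefore be read only from a contrast between arms, and the SAP states none at T8 or on change for any quantitative outcome. The T0 and T8 data permit a valid comparison, but the stated analysis does not use the randomisation.

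A reader could be misled in either direction:

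- If the shared diet works well, both arms improve significantly and a real added benefit of 16:8 is never tested.
- If power within each arm is moderate, one arm can be significant and the other not when the true effects are identical. This invites the conclusion that fasting works, or that it does not, from a contrast that is not a test of a difference.

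**Working it through.** **Step 1: what each named test compares**

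| Test in the SAP | What it compares | Time point | Contrasts the arms on a quantitative outcome after treatment? |
|---|---|---|---|
| Kolmogorov–Smirnov | Data against a normal distribution | Not stated | No |
| Chi-square | Categorical variables, groups not stated | Not stated | No, categorical only |
| Mann–Whitney U | The two arms | T0 only | No |
| Wilcoxon | T0 against T8 within patients | T0 and T8 | No |

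The Protocol contains no analysis text that adds to this list.

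**Step 2: what the Wilcoxon test can pick up**

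Let D be the effect of the shared diet, T any time trend, and F the added effect of 16:8. Let w be the share of patients in the 16:8 arm (the allocation ratio is not stated). Mean change is then:

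- energy-restricted arm: D + T
- 16:8 arm: D + T + F
- all patients pooled: D + T + wF

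Only the difference between arms isolates the target: (D + T + F) − (D + T) = F. Neither reading of the Wilcoxon sentence forms that difference.

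**Step 3: illustration when 16:8 adds nothing (F = 0)**

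The documents give no sample size, SD, effect or power, so there is no figure to reproduce. The 0.05 level is the SAP's. Two-sided testing, n per arm and normal changes with SD 1 are assumptions.

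If each arm has power p for its own Wilcoxon test and the true changes are equal, P(exactly one arm significant) = 2p(1 − p):

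- p = 0.05: 2 × 0.05 × 0.95 = 0.095
- p = 0.5: 2 × 0.5 × 0.5 = 0.50, the maximum
- p = 0.8: 2 × 0.8 × 0.2 = 0.32
- p = 0.9: 2 × 0.9 × 0.1 = 0.18

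Simulation, 4000 trials per setting, signed-rank test in each arm:

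| n per arm | True change, both arms (SD) | Power in one arm | Exactly one arm significant | Mann–Whitney on change significant |
|---|---|---|---|---|
| 15 | 0.3 | 17% | 28% | 3.9% |
| 15 | 0.5 | 41% | 49% | 5.0% |
| 15 | 0.8 | 80% | 33% | 4.9% |
| 20 | 0.3 | 24% | 38% | 5.6% |
| 20 | 0.5 | 55% | 50% | 5.6% |
| 20 | 0.8 | 91% | 16% | 4.6% |
| 30 | 0.3 | 35% | 46% | 4.8% |
| 30 | 0.5 | 73% | 39% | 4.0% |
| 30 | 0.8 | 98% | 3% | 5.2% |
| 50 | 0.5 | 93% | 15% | 5.2% |
| 50 | 0.8 | 100% | 0% | 5.1% |

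The between-arm test stays near its nominal 5%. The split in within-arm significance runs from 0% to 50%.

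**Step 4: illustration when 16:8 does add something**

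True changes of 1.0 SD (diet) and 1.8 SD (diet plus 16:8), same assumptions:

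| n per arm | Both arms significant | Mann–Whitney on change, power | Normal approximation |
|---|---|---|---|
| 20 | 98.8% | 66.7% | 71.6% |
| 30 | 100% | 84.4% | 87.3% |
| 50 | 100% | 97.2% | 97.9% |

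The last column follows from Φ(0.8/√(2/n) − 1.96). For n = 30 this is Φ(3.098 − 1.96) = Φ(1.138) ≈ 0.87.

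For smaller benefits the between-arm power at n = 15/20/30 falls to 24/33/46% (1.0 vs 1.5 SD) and 11/13/20% (1.0 vs 1.3 SD).

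**The case against.** The SAP is one short paragraph in the past tense. Its silence shows that no between-arm outcome test is stated, not that none was or will be run. The chi-square sentence is open enough to cover a categorical comparison at T8. Medians and quartiles, if given by arm, would let a reader see a larger change in one arm. The SAP nowhere says that 16:8 will be judged by setting one arm's p-value against the other's, so the 2p(1 − p) figures describe a misreading, not the error rate of a stated procedure. A significant pooled Wilcoxon is a correct finding of change and misleads only if credited to 16:8. Every size above rests on assumed inputs. A between-arm test may also be inconclusive, and testing many outcomes at 0.05 brings multiplicity.

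Much of this stands as a limit on the size of the harm. The illustrations should not be quoted as this trial's error rates, and the two harms mostly arise at different effect sizes. The multiplicity point is also fair. The Protocol (Measurements) names FGF-21, Beclin-1, ATG-5, steatosis, fibrosis and body composition; if these were six independent tests, 1 − 0.95⁶ = 26% of trials would show at least one false positive.

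None of it supplies the missing comparison. A plan is judged on what it commits to, and this one confines Mann–Whitney to baseline. The Protocol names no categorical effectiveness outcome for chi-square to act on. Descriptive medians give neither a test nor an interval for the difference. Low power for a small benefit argues for reporting the interval, not for omitting the comparison.

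**Conclusion.** The concern holds. Followed as written, the plan yields no test and no estimate of the only randomised contrast for any quantitative outcome. This is a wrong analysis for the design rather than missing detail, and it must be corrected before any statement about 16:8 is made. The conclusion rests on the text alone.

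Its numerical size is conditional on assumed sample sizes, normal changes and assumed effects. Under those assumptions, anywhere from 0% to 50% of trials with no 16:8 effect show significance in just one arm. A true 0.8 SD benefit on top of a 1.0 SD diet effect is masked by two significant within-arm results in almost every trial. The conclusion does not extend to categorical variables, where the SAP is too vague to judge.

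**What to change.** **Minimum.** State that, for each quantitative outcome, the arms are compared on T8-minus-T0 change by Mann–Whitney, with patients in the arm to which they were randomised. Report the Hodges–Lehmann difference and its 95% CI. State that Wilcoxon is run within each arm and is descriptive only. Base any statement about 16:8 on the between-arm estimate.

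**Preferred.** Regress T8 on arm with T0 as covariate (ANCOVA), on the log scale or in rank-based form if the data are skewed, and report the adjusted arm difference with 95% CI.

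**Needed alongside.** Give the number of missing T8 values by arm and how they are handled. Name the groups and time point for chi-square. Because several outcomes will now be tested between arms, name one as primary, or present them all as exploratory. If results have already been seen, only the second is credible.

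**Cost.** A few sentences in the SAP and one further SPSS procedure repeated for each outcome, with somewhat more work for the covariate-adjusted version. No new patients or measurements are needed. The SAP is written in the past tense; if the analysis is complete, the added comparison must be labelled post hoc.

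### Does relying on a paired Wilcoxon test confine the results to diet completers and so bias them?

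*SAP*

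**What the plan says.** The Protocol's Design section sets up a randomised comparison: "Patients who voluntarily agreed to participate in the study were randomly assigned into two groups". One arm follows an energy-restricted diet for 8 weeks. The other follows the same diet and also confines eating to 8 hours a day. There are two assessments only, and the section states that "Fibroscan investigations were performed before the intervention (T0) and after the intervention (T8". No adherence condition is attached to the second.

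The SAP is a single paragraph. For change over time, the "before/after comparison of the quantitative data was performed using the Wilcoxon test". For group comparison: "The Mann–Whitney U test was used to determine whether the baseline values were similar between the two groups before the intervention". It adds "Categorical variables were analyzed using the chi-square test", without saying which variables are meant.

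Neither document mentions an analysis population, missing values, imputation, an expected dropout rate or follow-up of patients who stop the diet. Neither says that any patient was lost.

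**The concern.** A signed-rank test works on within-patient differences, so a patient without T8 contributes nothing. There is no intermediate visit from which to recover information. One arm carries an extra daily restriction, so it is reasonable to ask whether retention might differ between arms and depend on how well the diet was working. If poor responders left, the change among those remaining would look better than the change in everyone randomised. With unequal losses, any contrast drawn between the arms would be distorted too. Nothing in the SAP guards against this, and the obvious remedy appears to be an intention-to-treat statement with multiple imputation of missing T8 values.

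**Working it through.** **Is there a figure in the plan to reproduce?** No. The documents give no sample size, SD, effect size or dropout rate. Every numerical input below is therefore an assumption.

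**Size of the bias if loss depends on response.** Let f be the share without T8 and r the correlation between poor response and being lost. Under a normal selection model, the mean change among those measured is overstated, in SDs of change, by

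bias = r × φ(q) / (1 − f), where q = z(1 − f).

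| f | q | φ(q) | φ(q)/(1 − f) | r = 0 | r = 0.3 | r = 0.5 | r = 1 |
|---|---|---|---|---|---|---|---|
| 0 | – | – | 0 | 0 | 0 | 0 | 0 |
| 0.1 | 1.282 | 0.1755 | 0.195 | 0 | 0.058 | 0.097 | 0.195 |
| 0.2 | 0.842 | 0.2800 | 0.350 | 0 | 0.105 | 0.175 | 0.350 |
| 0.3 | 0.524 | 0.3477 | 0.497 | 0 | 0.149 | 0.248 | 0.497 |

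For a contrast between arms at r = 0.5, losses of 20% against 10% give 0.175 − 0.097 = 0.078 SD. Losses of 30% against 10% give 0.248 − 0.097 = 0.151 SD.

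**Effect on the test.** The two-sided signed-rank test at 0.05 was simulated with no true change, 20 to 50 patients randomised per group and 4,000 runs per setting. Rejection rates were:
- no loss, or loss unrelated to response: about 0.04 to 0.05;
- 10% lost, r = 0.3 to 0.5: 0.05 to 0.10;
- 20% lost, r = 0.3 to 0.5: 0.07 to 0.21;
- 30% lost, r = 0.3 to 0.5: 0.08 to 0.32.

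The mechanism is real, but it needs two conditions together: some T8 values missing, and missingness related to response. The documents establish neither.

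**Who would be in the test?** Having T0 and T8 values is not the same as completing the diet. The Design section places a measurement at T8 and does not restrict it to adherent patients. If all randomised patients attend, the pairs are the randomised groups.

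**Would imputation help?** Take the case with f = 0.2 and r = 0.5, where the bias among those measured is about 0.175 SD. Impute T8 by regression on T0 within an arm, with an assumed correlation between T0 and change:

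| Correlation of T0 with change | Bias after imputation (SD) | Share remaining |
|---|---|---|
| 0 | about 0.175 | 100% |
| 0.3 | about 0.160 | about 92% |
| 0.5 | about 0.135 | about 77% |

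The imputed values are borrowed from patients who stayed, and who responded better at the same T0. With only two assessments, nothing else is available within these measurements to correct for that.

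**The case for a change.** The strongest case for a change is that the SAP text is complete prose, not redacted, and leaves patients with both measurements as the default set. The added restriction in one arm makes unequal, response-related loss plausible. A few sentences would close the gap: analysis by assigned arm, T8 sought regardless of adherence, a missing-data rule and counts by arm. Even if data collection is over, the population rule and the counts could still be supplied.

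Much of this stands. The silence is genuine, the bias formula suits the mechanism, and those sentences would be good practice. Three parts do not carry the weight placed on them.

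- An extra restriction is evidence of burden. It is not evidence of missing data or of loss that depends on response. Patients who leave because the schedule is inconvenient, whatever their response, create no bias.
- The damage to an arm contrast concerns a test the SAP does not contain, since its Mann–Whitney comparison is confined to baseline. Whether the plan should include a between-arm outcome test is a separate question.
- The Wilcoxon test is not the source of the gap. Any test on observed T8 values, between or within arms, would omit the same patients.

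**Conclusion.** No change is called for. The plan leaves the analysis population and missing-data handling unwritten, but says nothing at odds with the usual practice of measuring every patient at T8, analysing each in the assigned arm and reporting how many were randomised and measured. An analyst can be expected to fill that gap sensibly.

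The bias is zero with no missing T8 values or with loss unrelated to response. It is about 0.10 to 0.25 SD within an arm at an assumed 20 to 30% loss with r between 0.3 and 0.5. None of those inputs comes from the documents. The one specific new method on offer, imputation from arm and T0, would remove at most about a quarter of the bias in the case examined (20% loss, r = 0.5, correlation of T0 with change up to 0.5), and might suggest the problem had been solved.

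This conclusion assumes that losses over 8 weeks are modest and are reported by arm. If the report showed substantial or clearly unequal losses, results from patients with both measurements should be read with the figures above in mind.
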